## 2 Research Methods

### 2.1 Overview of methods

This evaluation will be a mixed methods observational design with mainly descriptive and exploratory analysis. The desk research will review documents, secondary data public available (such as NFHS), and any App background data (deidentified) to better understand the programme.

This is followed by qualitative surveys for which 40 in-depth interviews of various beneficiaries and programme stakeholders (demand creators, service providers, lifestyle partners) will be conducted in person or over phone.

Depending on the insights, we will develop a structured quantitative questionnaire and administer the in-person survey to approx. 480 beneficiaries of SRH and MCH services (total). These surveys will seek information on knowledge, practices, barriers, enablers for SRH and MCH services, exposure o Tiko platform, and how it helped or did not help. The survey participants will be women (18-35years of age) who had subscribed to Tiko card between 2018 and 2020. A subset of these would be regular users, a subset will be sporadic

or one-time user and remaining will be 'non-users'. The sample will try to get adequate representation from all categories.

The in-person surveys will be followed with shorter (10-15 minutes) phone surveys with 1200 active users and 600 non-users who had enrolled on Tiko platform. Phone surveys will collect only basic information needed to confirm findings from in-person and qualitative surveys.

The analysis will triangulate the insights from both qualitative and quantitative analysis. We mainly anticipate descriptive analysis to tabulate indicators related to knowledge, practices, barriers, enablers w.r.t. SRH and MCH services, exposure and use of Tiko platform, how it has helped or not helped or affected their well being, suggestions and preferences for different components of the platform, etc. We anticipate cross tabulation by socio-economic characteristics, regions (say by Cities), and duration of use.

While no analytical tests are anticipated at this time, we expect to conduct standard bivariate tests (t-test and chi2 test) and regression analysis for more nuanced group mean tests or multiple comparison tests (logit, OLS, mixed models). We will be adjusting for standard errors for robust inference. In case of statistical inference, we expect one side test with alpha < 0.1 to consider a relationship or test statistic significant.

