#### 2.2 Sample Design and Power Calculations

For detailed 45-50 minutes in-person surveys, 570 respondents will be interviewed across Rajasthan, Uttar Pradesh and Delhi, of which we expect to complete 480 interviews. This sample size was determined on basis of measuring a proportion of 50% with 5 pp error rate and 95% confidence which yields n of 384 and this n was increased by design effect of 1.25 to account for clustering if any at the city level. In person surveys will be done in Agra, Jaipur

For phone surveys, we designed a sample of 2000 complete surveys. Moreover, over sampling will be done in Rajasthan, Uttar Pradesh and Delhi to ensure at least 50 interviews in each city. This sample is designed such that we can conduct descriptive analysis for 3-4 sub-groups (say by cities or by socio-economic categories) with at least 300-400 sample in

each sub-group. The purpose of phone surveys will be to add more statistical power to limited in-person sample size we have for few key questions of interest.

We also expect that the phone surveys and in-person data will be used for statistical group mean tests between regular users and one-time or non-users to compare SRH and ANC related practices between the two groups. It is not a controlled trial of Tiko platform but will be exploratory to understand additionality in service usage of regular users if any.

Assuming at least 150 regular and 150 non-users included in the in-person surveys, the sample will have power to detect 25% relative change or 0.25 SD change from an outcome distributed binomially with mean of 0.50 or with standardized normal distribution with mean 0 and SD of 1 N $^{\circ}(0,1)$  with power of 80% and Type I error of 0.10 with one sided test.

Assuming 500 regular and 500 non-users included in the in-person surveys, the sample will have power to detect 15% relative change or 0.15 SD change from an outcome distributed binomially with mean of 0.50 or with standardized normal distribution with mean 0 and SD of 1 N~(0,1) with power of 80% and Type I error of 0.10 with one sided test.

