#### 2.3 Sampling for In-Person and Phone-Surveys

The sample frame for both surveys will be the Tiko beneficiary database available with Triggerise. Below is the summary of viable database sample frame (exclude smaller sites where the programme is too small to be considered in this study)

Stata	City	Area	Number of		
Sidle			Enrollments	Actual Users	Non-Users
Uttar Pradesh	Agra	Both	34,726	21,743	12,983
Rajasthan	Jaipur	Both	29,588	28,531	1,057
Rajasthan	Ajmer	Urban	7,325	4,532	2,793
Rajasthan	Tonk	Peri Urban	5,176	3,993	1,183
Delhi	Delhi	Urban	3,846	3,142	704
Uttar Pradesh	Firozabad	Peri Urban	1,044	119	925
TOTAL			81,705	62,060	19,645

The following steps will be followed for sampling of in-person survey respondents:

- 1. Restrict the study to only Jaipur and Agra which constitutes 70% of the enrollments and 84% of the actual user base.
- 2. Stratify sample as 150 non-users (enrollment minus users) and 350 users
- 3. Distribute sample in approx. proportion to the actual numbers in both cities for users and non-users as below.

City	Non-users	Actual Users	Total
Agra	100	150	250
Jaipur	50	200	250
Total	150	350	500

- 4. Distribute the sample across the 'Tiko Pro Agents' working in the city. We currently don't have this data, but we expect to complete at least 5 interviews per agent and spread the sample to cover about 25% of the agents working in the city.
- 5. Based on above, randomly sample the Pro Agents from database that will be made available by Triggerise.
- 6. Obtain a list of randomly sampled Beneficiaries from Triggerise for each sampled pro agent. We will obtain 3-times the number of completed interviews required per agent because our scoping visit suggests expecting 30-40% response rate in finding the beneficiary house with help of agent and then getting their consent for the interview. If required, Triggerise will make available more beneficiaries (their name and phone numbers per agent) if the sample size is not achieved.
- 7. NEERMAN enumerators will call each beneficiary sequentially in the list and fix appointments for the in-person interview. The phone records will track validity of numbers, refusals, and consents. Pro agent's help will be sought to find address or in field logistics or to establish our enumerators' bona fides.

The following steps will be followed for sampling of phone-survey respondents:

- 1. Exclude Firozabad which has no programme in 2020

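### Section 2.2 credits the in-person survey with a 500 vs 500 comparison that it cannot contain, and the phone survey has two sizes (1,800 in section 2.1; 2,000 in sections 2.2 and 2.3)

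*Protocol*

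**What the plan says.** **Power statements.** Protocol section 2.2 gives two in succession, and both name the in-person survey.

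- The first begins "Assuming at least 150 regular and 150 non-users included in the in-person surveys" and claims 80% power for a 25% relative change from 0.50, or 0.25 SD.
- The second reads "Assuming 500 regular and 500 non-users included in the in-person surveys, the sample will have power to detect 15% relative change", or 0.15 SD, also with 80% power.
- Both use a one-sided test at 0.10.

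**In-person sample.** Section 2.1 gives about 480. Section 2.2 starts from 570 respondents, "of which we expect to complete 480 interviews". Section 2.3 instructs: "Stratify sample as 150 non-users (enrollment minus users) and 350 users", a total of 500, and its city table shows the same split.

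**Phone sample.** Section 2.1 plans "phone surveys with 1200 active users and 600 non-users who had enrolled on Tiko platform". Section 2.2 states: "For phone surveys, we designed a sample of 2000 complete surveys". Section 2.3 stratifies the phone sample into 500 non-users and 1,500 users.

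**Use of the data.** Section 2.2 expects that "the phone surveys and in-person data will be used for statistical group mean tests between regular users and one-time or non-users".

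**The concern.** The second power statement needs 1,000 interviews, 500 of them with non-users. The survey it names has about half that total and fewer than a third of those non-users. A reader who relies on section 2.2 would believe that the in-person survey can detect 0.15 SD with 80% power.

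The phone survey also carries two totals and two splits, so its target could be 1,800 or 2,000 interviews, with 600 or 500 non-users. These are stated design quantities behind the comparison of regular users with one-time users or non-users, and the protocol plans to publish the findings.

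**Working it through.** **Inputs.** Group sizes, effects, alpha and power come from section 2.2. In-person strata come from section 2.3. Phone sizes come from sections 2.1, 2.2 and 2.3.

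**Formula.** For a difference of d SD, one-sided alpha 0.10 and no design effect:

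power = Φ( d / √(1/n₁ + 1/n₂) − 1.2816 )

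**Step 1: reproduce the plan's own figures.**

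- 500 vs 500, d = 0.15: √(2/500) = 0.0632; 0.15/0.0632 = 2.372; 2.372 − 1.282 = 1.090; power 86%. For proportions, 0.50 vs 0.575, it is also 86%.
- 150 vs 150, d = 0.25: √(2/150) = 0.1155; 0.25/0.1155 = 2.165; 2.165 − 1.282 = 0.883; power 81%. For 0.50 vs 0.625 it is 82%.

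Both statements reach the claimed 80% for the group sizes they assume.

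**Step 2: put the in-person sample into the 0.15 SD claim.**

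| Users or regular users vs comparator | Power for 0.15 SD |
|---|---|
| 150 vs 150 | 51% |
| 350 vs 150 (planned strata) | 60% |
| 240 vs 240 (480 completes) | 64% |
| 250 vs 250 (500 interviews) | 65% |

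For 350 vs 150: √(1/350 + 1/150) = 0.0976; 0.15/0.0976 = 1.537; 1.537 − 1.282 = 0.255; power 60%. This counts every user as regular. Section 2.1 makes regular users only a subset, so 60% is an upper bound for regular users vs non-users.

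The equal splits are not planned allocations. They serve as a ceiling, because for a fixed total 1/n₁ + 1/n₂ is smallest when the groups are equal. The ceiling matters because section 2.2 lets one-time users join the comparator. Even so, no division of 500 interviews passes 65%. The effect detectable with 80% power at 250 vs 250 is (1.2816 + 0.8416) × √(2/250) = 0.19 SD.

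**Step 3: put the phone sample into the same claim, all users counted.**

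- 500 vs 1,500: √(1/500 + 1/1,500) = 0.0516; 0.15/0.0516 = 2.905; 2.905 − 1.282 = 1.623; power 95%.
- 600 vs 1,200: √(1/600 + 1/1,200) = 0.0500; 0.15/0.0500 = 3.000; 3.000 − 1.282 = 1.718; power 96%.

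Both are upper bounds if only some users are regular.

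**Step 4: compare the phone totals.**

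- Section 2.1: 1,200 + 600 = 1,800.
- Section 2.2: 2,000.
- Section 2.3: 1,500 + 500 = 2,000.

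Section 2.1 therefore has 200 fewer interviews overall: 300 fewer users and 100 more non-users.

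**The case against.** The strongest reply is that the first part is a one-word slip. The sentence just before it already gives a workable in-person power statement. Section 2.2 calls the in-person sample limited and says that the phone survey is there to add power. The only stratum of 500 non-users is in the phone survey. The phone conflict sits in an overview section, while sections 2.2 and 2.3, which set out the design and sampling, agree on 2,000. The study is mainly descriptive and exploratory.

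Most of this stands, and it makes the consequence minor. It does not remove the contradictions. Section 2.2 uses both surveys for these tests, so only the sponsor can say which data the 500 vs 500 sentence describes. A looser use of the word for users might blur the two user counts, but it cannot turn 500 non-users into 600.

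Three stronger readings are tempting, and the documents do not support them.

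- *The power calculation is wrong.* It is not: 500 vs 500 gives 86%, above the claimed 80%.
- *The phone survey is too small.* With all users counted, both versions give about 95% or more for 0.15 SD.
- *The two power statements use different design effects.* Section 2.2 says "this n was increased by design effect of 1.25 to account for clustering if any at the city level", but only for the precision calculation (384 × 1.25 = 480). Neither power statement invokes it, and both hold without it. Because 500 per group happens to give 80% with a factor of 1.25, a mixed convention might be inferred, but the text does not show one.

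**Conclusion.** The point holds as two internal inconsistencies of minor consequence.

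First, the survey named in the 500 vs 500 statement cannot deliver the stated 80%. Its power for 0.15 SD is about 60% on the planned strata and at most 65% on any split of 500. That the phone survey was meant is a probable inference, not something the text states. If it was, the statement also needs at least 500 regular users among the phone users, a number that the protocol does not give.

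Second, the phone sample is stated as both 1,800 and 2,000, with 600 or 500 non-users, and nothing reconciles the two.

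The figures assume a one-sided test at 0.10, independent observations and no design effect. What is at stake is a wrongly attributed power and an ambiguous phone target, not the adequacy of either sample for its plausible purpose: 0.25 SD for the in-person survey and 0.15 SD for the phone survey.

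**What to change.** - **Section 2.2:** the sponsor confirms which survey, or combination of surveys, the 500 vs 500 statement describes and corrects the label. The 150 vs 150, 0.25 SD statement stays as the in-person one.
- **Section 2.1:** align the phone sample with the 2,000 (1,500 users and 500 non-users) in sections 2.2 and 2.3, or state one other allocation throughout.
- **Optional:** note that applying the in-person design effect of 1.25 to the 150 vs 150 statement would give about 74% (2.165/√1.25 = 1.936; 1.936 − 1.282 = 0.655).

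The cost is wording only: one label and one sentence. If the 2,000 allocation is kept, neither the samples nor the city tables change.

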#### 2.3 Sampling for In-Person and Phone-Surveys

The sample frame for both surveys will be the Tiko beneficiary database available with Triggerise. Below is the summary of viable database sample frame (exclude smaller sites where the programme is too small to be considered in this study)

Stata	City	Area	Number of		
Sidle			Enrollments	Actual Users	Non-Users
Uttar Pradesh	Agra	Both	34,726	21,743	12,983
Rajasthan	Jaipur	Both	29,588	28,531	1,057
Rajasthan	Ajmer	Urban	7,325	4,532	2,793
Rajasthan	Tonk	Peri Urban	5,176	3,993	1,183
Delhi	Delhi	Urban	3,846	3,142	704
Uttar Pradesh	Firozabad	Peri Urban	1,044	119	925
TOTAL			81,705	62,060	19,645

The following steps will be followed for sampling of in-person survey respondents:

- 1. Restrict the study to only Jaipur and Agra which constitutes 70% of the enrollments and 84% of the actual user base.
- 2. Stratify sample as 150 non-users (enrollment minus users) and 350 users
- 3. Distribute sample in approx. proportion to the actual numbers in both cities for users and non-users as below.

City	Non-users	Actual Users	Total
Agra	100	150	250
Jaipur	50	200	250
Total	150	350	500

- 4. Distribute the sample across the 'Tiko Pro Agents' working in the city. We currently don't have this data, but we expect to complete at least 5 interviews per agent and spread the sample to cover about 25% of the agents working in the city.
- 5. Based on above, randomly sample the Pro Agents from database that will be made available by Triggerise.
- 6. Obtain a list of randomly sampled Beneficiaries from Triggerise for each sampled pro agent. We will obtain 3-times the number of completed interviews required per agent because our scoping visit suggests expecting 30-40% response rate in finding the beneficiary house with help of agent and then getting their consent for the interview. If required, Triggerise will make available more beneficiaries (their name and phone numbers per agent) if the sample size is not achieved.
- 7. NEERMAN enumerators will call each beneficiary sequentially in the list and fix appointments for the in-person interview. The phone records will track validity of numbers, refusals, and consents. Pro agent's help will be sought to find address or in field logistics or to establish our enumerators' bona fides.

The following steps will be followed for sampling of phone-survey respondents:

- 1. Exclude Firozabad which has no programme in 2020
- 2. Stratify sample as 500 non-users (enrollment minus users) and 1500 users
- 3. Distribute sample in proportion to the actual numbers as below.

City	Non-users	Actual Users	Total
Agra	347	527	873
Jaipur	28	691	719
Ajmer	75	110	184
Tonk	32	97	128
Delhi	19	76	95
Total	500	1500	2000

- 4. Obtain a list of randomly sampled Beneficiaries as above. We will obtain 10-times the number of completed interviews required per agent because our scoping visit suggests to expect 10-15% response rate in phone surveys. If required, Triggerise will make available more beneficiaries (their name and phone numbers per agent) if the sample size is not achieved.
- 5. NEERMAN enumerators will call each beneficiary sequentially in the list and fix appointments for the phone interview. The phone records will track validity of numbers, refusals and consents. Pro agent's help will be sought to establish our enumerators' bona fides if needed.

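### User status builds up over unequal time since enrolment, and the plan does not secure the enrolment date needed to separate the two in the user-type comparison

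*Protocol*

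**What the plan says.** Section 2.1 of the protocol sets the population: "The survey participants will be women (18-35years of age) who had subscribed to Tiko card between 2018 and 2020". Section 2.3 sets the frame: "The sample frame for both surveys will be the Tiko beneficiary database available with Triggerise". It then fixes the strata, "Stratify sample as 150 non-users (enrollment minus users) and 350 users" for the in-person survey and "Stratify sample as 500 non-users (enrollment minus users) and 1500 users" for the phone survey.

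Below the user level, section 2.1 names types without a frequency or a time window: "A subset of these would be regular users, a subset will be sporadic" or one-time users, and the remainder non-users.

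Section 2.2 says what the groups are for: "statistical group mean tests between regular users and one-time or non-users to compare SRH and ANC related practices between the two groups". It calls this exploratory, aimed at any additional service use among regular users, and gives power for it.

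On data, the beneficiary lists in section 2.3 are described as names and phone numbers. The platform data in sections 2.1 and 2.6 are described as city, age and the details of each transaction, including its date. Enrolment date appears in neither list.

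**The concern.** A woman who joined in late 2020 and has not yet bought falls in the same stratum as one who joined in 2018 and never bought. A woman with one purchase in 2018 remains a user however long ago that was. No common follow-up is set, so time since enrolment differs between the strata to an unknown degree.

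Two things can follow in the comparison of SRH and ANC practices. Some non-users may be users-to-be, which dilutes the contrast. And if these practices vary with time since enrolment or with the year of joining, a difference can appear, or be hidden, with no contribution from the platform.

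The planned tabulation by length of use does not help, because a non-user has no length of use. Nor do transaction dates stand in for enrolment date, because a non-user has no transactions. If the enrolment date is not requested when the lists are drawn, a later adjustment is not secured.

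**Working it through.** **1. The plan's own figures.** Enrolments minus users equals the stated non-users in every city in the section 2.3 table. Non-user shares are Agra 12,983/34,726 = 37.4%, Jaipur 1,057/29,588 = 3.6%, and all cities 19,645/81,705 = 24.0%.

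Power for a mean difference is Φ(δ√(n/2) − 1.2816), with one-sided alpha 0.10:
- 150 v 150, δ = 0.25: Φ(2.165 − 1.282) = 81.2%. For proportions 0.50 v 0.625 it is 81.8%.
- 500 v 500, δ = 0.15: 86.2%. For proportions it is 86.4%.

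The stated 80% is met, so the point is not a calculation error.

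**2. How many non-users could be merely recent?** The documents give no enrolment dates, extract date or purchase timing, so this is illustration only. Assume enrolment uniform over 36 months, exponential time to first purchase with median M months among eventual users (λ = ln 2/M), and status read L months after enrolment closes.

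- Share of eventual users who have not yet bought: q = (e^(−λL) − e^(−λ(L+36)))/(36λ)
- Share of eventual users, given observed non-user share s: c = (1 − s)/(1 − q)
- Share of non-users who are merely recent: m = cq/s

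Example (all cities, L = 0, M = 3): λ = 0.231, q = 0.120, c = 0.760/0.880 = 0.863, m = 0.863 × 0.120/0.240 = 43%.

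| L | M | m, all cities | m, Agra | Mean months since enrolment in Agra, users v non-users |
|---|---|---|---|---|
| 0 | 1 | 13% | 7% | 18.7 v 16.8 |
| 0 | 3 | 43% | 23% | 19.9 v 14.9 |
| 0 | 6 | 98% | 52% | 21.1 v 12.9 |
| 6 | 1 | 0.2% | 0.1% | 24.0 v 24.0 |
| 6 | 3 | 10% | 5% | 24.4 v 23.3 |
| 6 | 6 | 42% | 22% | 25.3 v 21.8 |

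Agra is the more relevant column. It supplies 100 of 150 in-person and 347 of 500 phone non-users.

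**3. Check against Jaipur.** With L = 0 and M = 1, q = 4.0%, which already exceeds Jaipur's total non-user share of 3.6%. The model cannot hold there with status read at the end of enrolment, unless first purchase is faster than a one-month median. Slow uptake with an early extract is therefore ruled out for Jaipur, which supplies 50 of 150 in-person and 28 of 500 phone non-users.

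**4. What it could do to the test.** If a share m of non-users are users-to-be who resemble users (assumed), δ becomes δ(1 − m):

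| m | 150 v 150 | 500 v 500 |
|---|---|---|
| 0 | 81% | 86% |
| 10% | 75% | 80% |
| 20% | 67% | 73% |
| 30% | 59% | 65% |

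Conversely, suppose there is no platform effect but time since enrolment alone raises a 50% outcome among regular users (assumed). A shift of 2 points makes the one-sided 0.10 test reject in 17% (150 v 150) or 26% (500 v 500) of cases. A shift of 5 points gives 34% or 62%. A shift the other way would push rejection below 10% and could mask a real difference.

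**The case against.** The best defence is that the effect may be trivial. Section 1.2 says that the agent both brings the woman onto the platform and links her with services, so first purchase may come at enrolment. Jaipur's low non-user share fits that. The protocol also describes the study as mainly descriptive and this comparison as exploratory, not a controlled trial. Regression is anticipated, the covariates may be set in an analysis plan that is not shown, and the questionnaires, also not shown, may ask when the woman joined.

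Most of this stands as a limit on size. It does not remove the problem: section 2.2 powers this contrast, and covariates in an analysis plan can be used only if the enrolment date is obtained. The sampling rule and the data to be supplied are fixed in the protocol itself.

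Four stronger readings are tempting and are not supported:

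- **Firozabad as proof.** Its non-user share is 925/1,044 = 88.6%, but the plan says "Exclude Firozabad which has no programme in 2020" for the phone survey and limits the in-person survey to Agra and Jaipur. It enters no comparison. With no programme in 2020, its figure more plausibly reflects absent services than short follow-up.
- **One-time users are mostly women who joined late.** No rule for assigning one-time or regular is given. It could come from the interview, since section 1.3 asks how often women used the platform. That part is inference from a missing definition.
- **Questions on not returning become meaningless.** They are descriptive questions within a group, and a woman can answer that she has only just joined.
- **Recent enrollees must be excluded at sampling.** Nothing in the documents requires it, and they are useful for the descriptive tables.

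**Conclusion.** The point holds on the text. Status is cumulative over women who subscribed across three years, no common follow-up is set, and neither the tabulation by length of use nor the listed data can separate user type from enrolment cohort.

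Its size is unknown. It is negligible if first purchase is prompt or the extract is well after enrolment, and large if uptake is slow and the extract is early. Dilution and a spurious difference are both possible, so the sign of any bias is not fixed. Every figure beyond the frame shares and the reproduced power rests on assumed uptake, enrolment pattern and outcome trend.

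This is a cheap improvement to make before the lists are drawn. It does not invalidate the survey.

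**What to change.** - **Section 2.3, in-person step 6 and phone step 4:** have the sponsor supply, with each sampled name, the enrolment date and either transaction dates or user type assigned by a stated rule.
- **User-type comparison (sections 2.2 and 2.6):** stratify by or adjust for enrolment date. This deals with cohort differences but not with users-to-be counted as non-users.
- **Sensitivity analysis for the latter:** restrict to women with a common minimum follow-up, for example enrolled at least 12 months before the extract, and define user type by transactions in that same window after enrolment. Twelve months is a reasonable choice, not one the documents dictate.
- **Sampling:** keep recent enrollees in the sample and in the descriptive tables.

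**Cost.** The change needs one more linked variable from the sponsor, who presumably holds it already, since the 2018 to 2020 criterion depends on it. The platform data are described as carrying no identifiers, so the link to sampled names should be added to the data-handling text.

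The sensitivity sample will be smaller, and tightest for Jaipur non-users. In-person names come from about 25% of agents, so if non-users are evenly spread about 0.25 × 1,057 = 264 are reachable, against 3 × 50 = 150 names needed. That leaves about 114 spare (43%), before the 18-35 age limit, so there is limited room to top up that cell with women enrolled longer.
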